2.2. Specific Aims

The specific aims of the PROP research program are:

- To evaluate if a series of quantitative respiratory assessments performed prior to NICU discharge in extremely preterm infants will predict symptomatic respiratory disease and health care utilization during the first year of life more accurately than the current clinical or physiological diagnoses of BPD.
- 2. To create a biospecimen repository for preterm infants, by collecting DNA from PROP study participants and their parents and by obtaining tracheal aspirate and urine samples from infants at pre-specified postnatal ages, that can be used to stratify patient populations based upon molecular as well as clinical phenotypes.
- 3. To collect detailed descriptive data on respiratory medication exposures in extremely preterm infants from birth through 1 year of age in order to understand the variability of current prescribing practice and its relationship to respiratory morbidity.
- 4. To create a multi-center core database containing prospectively collected, standardized, clinical data and to test for associations between these clinical parameters and the novel, putative biomarkers with the goals of quantifying severity, refining diagnosis and prognosis, and identifying mechanisms of causation of respiratory disease in preterm infants.
- 5. To assess pulmonary physiologic outcomes at 1 year of age by infant pulmonary function testing (iPFT) in a subset of infants to identify associations between standard measurements of lung function at 1 year and the quantitative and qualitative assessments of respiratory function and morbidity between 36 weeks PMA and 1 year of age.

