2.1. Primary Outcome: Post-prematurity Respiratory Disease

The primary goal of the PROP studies (single center and multicenter protocols) is to identify biomarkers (biochemical, physiological and genetic) and clinical variables that are associated with and thus potentially predictive of pulmonary status in preterm infants up to 1 year corrected age. An objective and validated measure of pulmonary outcome at 1 year does not currently exist. Some promising measures are in development but not yet ready for use in a multi-center large clinical study. For example, reduced alveolar number is a key pathologic feature of BPD .²¹ Physiologically, this is reflected in decreased diffusion capacity of the lung to carbon monoxide (DLCO), and infants with BPD have lower DLCO compared to healthy full term controls.²² However, measurement of infant DLCO in a multi-center study is not feasible in PROP because of the lack of standardized equipment, the need for C¹⁸O instead of standard CO, and the need for a mass spectrometer to measure CO instead of a standard infrared sensor.²³

Moreover, the PROP investigators firmly believe that the burden of chronic respiratory illness on the infants and their families is of utmost importance. Therefore, we propose a composite primary outcome of morbidity that is based on serial parental reports of respiratory symptoms, medications, hospitalizations and dependence on technology during the first year of life.

Data collection for the outcome assessment will be based on interviews conducted with the infant's main caregiver at 3, 6, 9 and 12 months corrected age. The time frame for data collection is based on questions "since last contact." Numerous epidemiological studies of asthma have used parental or self report of symptoms, physician-diagnosed asthma and allergies, or the use of medications (which may abrogate symptoms) as critical outcomes.^{16, 24-26} Recent studies have most commonly employed the International Study of Asthma and Allergies in Childhood (ISAAC) questionnaire.²⁷ These studies have collected data regarding 1 year old children, although not children before one year of age. The questionnaire to be utilized in PROP has been modified from the Tucson Children's Respiratory Study (CRS)^{20, 28-31} and the Breathing Outcomes Study. The latter is an ancillary study for the NICHD Neonatal Research Network (NRN) Surfactant Positive Airway Pressure and Pulse Oximetry Trial (SUPPORT).

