Survey items selected for the determination of the primary outcome will be focused on the following four domains, with any positive response to any element identifying morbidity:

- 1. **Respiratory medications**: inhaled bronchodilators, inhaled steroids, systemic steroids, methylxanthines, diuretics, pulmonary vasodilators
- 2. Hospitalizations for cardiopulmonary causes: any hospitalization regardless of duration
- 3. Symptoms: any wheeze, cough without cold
- 4. **Home technology dependence**: use of home oxygen, ventilator or CPAP/BiPAP of any durations since last contact

A late death after a postmenstrual age of 36 weeks from cardio-respiratory failure will also meet the definition of PRD.

The primary outcome will be dichotomous, and defined as "No substantial post-prematurity respiratory disease" or "Post-prematurity respiratory disease." To be classified as having post-prematurity respiratory disease, infants must have a positive response in at least 1 of 4 morbidity domains during at least 2 separate parental interviews. Quarterly data collection up to 1 year corrected age will allow us to identify phenotypes based on the trajectory of post-prematurity respiratory disease and how these different trajectories predict later lung function and the diagnosis of asthma, if we continue to follow this cohort of children.

Follow up data from recently published randomized controlled trials and observational studies in similar but not identical populations of very preterm infants suggest that the incidence of this primary outcome will be at least 30% and possibly as high as 60%.³²⁻³⁵

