3.1.2. Daily Medication Data

Data on all commonly used classes of drugs in the neonatal intensive care unit will be collected. For most drugs, the research coordinator will simply record whether or not a particular drug was administered.

However, with additional resources obtained as a supplement from the Eunice Kennedy Shriver National Institute of Child Health and Development (NICHD) under the Best Pharmaceuticals for Children Act, four classes of commonly used respiratory drugs will be studied more extensively with respect to dose and administration, duration of use and adverse effects: diuretics, inhaled bronchodilators, methylxanthines, inhaled and systemic corticosteroids. The PROP investigators will collect detailed data on these specific respiratory medication exposures from birth to one year corrected age in this prospective multi-center cohort of very preterm infants. In the NICU, the daily data collected from the medical record and will include name of medication, route of administration, dose and frequency. This will provide much needed insights into the current use of respiratory drugs in this high-risk population. There are no current evidence-based practice guidelines for most of the respiratory medications that are used in preterm infants. Moreover, the great majority of these respiratory medications are prescribed for this population "off-label". Understanding current drug prescribing practice and its potential variability in this vulnerable population of children will have important implications for the design of future clinical research studies in sick and preterm newborns who are at risk of developing chronic respiratory disease.

3.1.3. **Collection of Biospecimens for a PROP Repository**

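### For drugs used after discharge, the Aim 3 association with PRD is partly created by definition, because PRD counts the same drugs from the same interviews

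*Protocol*

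**What the plan says.** **Aim 3 (Protocol 2.2)** is to collect descriptive data on respiratory drug exposure in order to "understand the variability of current prescribing practice and its relationship to respiratory morbidity". Section 3.1.2 sets the window as "respiratory medication exposures from birth to one year corrected age in this prospective multi-center cohort of very preterm infants" and names the classes studied in detail: "diuretics, inhaled bronchodilators, methylxanthines, inhaled and systemic corticosteroids". Exposure has two sources. Section 3.1.2 describes the inpatient source as "In the NICU, the daily data collected from the medical record". After discharge, section 3.3.1 has parents report medications at the follow-up contacts.

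**PRD (2.1)** rests on interviews with the "main caregiver at 3, 6, 9 and 12 months corrected age". Its first domain lists "inhaled bronchodilators, inhaled steroids, systemic steroids, methylxanthines, diuretics, pulmonary vasodilators". The element rule is "with any positive response to any element identifying morbidity", and the classification rule is that "infants must have a positive response in at least 1 of 4 morbidity domains during at least 2 separate parental interviews". Late cardio-respiratory death also qualifies.

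**Related outcomes.** The severity score (4.3.3) is built on the same four domains. Section 4.3.4 gives an open list of PRD variants: a per-visit morbidity indicator, a changed frequency requirement, and re-weighting of components. None of the listed variants leaves medications out. Outcomes without drugs do exist: respiratory re-hospitalization as a component (4.4.2, 4.8.1), the physical examination score (4.3.2), and FEF75 in the iPFT subset (4.8.2). The protocol assigns none of them to Aim 3.

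**The concern.** If the exposure is itself an item of the outcome, the two are associated whether or not the drug has anything to do with disease. Aim 3 rests on the premise that prescribing varies, and section 3.1.2 says that most of these drugs lack evidence-based guidelines. Where habit rather than illness drives prescribing after discharge, heavier prescribing raises PRD directly. It can then look like greater morbidity, or like an adverse relation with the drug. Section 4.7.1 plans explicit comparisons between centres, so the same mechanism could pass for a centre difference in respiratory disease.

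**Working it through.** The protocol gives no figure for Aim 3, so there is none to reproduce. The check compares the definitions and then sizes the built-in association under stated assumptions.

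**1. Drug lists.**

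| Studied in detail (3.1.2) | PRD domain 1 (2.1) |
|---|---|
| Diuretics | Yes |
| Inhaled bronchodilators | Yes |
| Methylxanthines | Yes |
| Inhaled and systemic corticosteroids | Yes, as two entries |
| (not in the list) | Pulmonary vasodilators |

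The overlap is complete for the four studied classes.

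**2. Time and source.** Post-discharge exposure and PRD come from the same interviews at 3, 6, 9 and 12 months. NICU exposure comes from charts before that period and is not a PRD item.

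**3. Built-in association after discharge.** Assumptions, not protocol figures: four independent interviews; probability m of a studied drug at each; probability q of any non-drug domain at each; drugs unrelated to the non-drug domains. The chance that an interview is positive is r = 1 − (1 − m)(1 − q), and PRD = 1 − (1 − r)⁴ − 4r(1 − r)³.

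Worked case, m = 0.10 and q = 0.20:
- r = 1 − 0.90 × 0.80 = 0.28, so PRD = 31.3%.
- Infants with no drug at any interview: PRD = 1 − 0.8⁴ − 4 × 0.2 × 0.8³ = 18.1%.
- Infants with any drug: a share of 1 − 0.9⁴ = 34.4%. Their PRD is (0.313 − 0.656 × 0.181)/0.344 = 56.6%.
- Odds ratio = (0.566/0.434)/(0.181/0.819) = 5.9.
- Infants with a drug at two or more interviews: PRD = 100%.

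Scenarios with m from 0.05 to 0.20 and q from 0.10 to 0.25, kept where PRD lies within the protocol's 30% to 60%:

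| m | q | PRD | Odds ratio, any vs no drug | PRD without domain 1 |
|---|---|---|---|---|
| 0.05 | 0.25 | 33% | 4.4 | 26% |
| 0.10 | 0.20 | 31% | 5.9 | 18% |
| 0.10 | 0.25 | 39% | 5.1 | 26% |
| 0.20 | 0.10 | 31% | 17.7 | 5% |
| 0.20 | 0.15 | 38% | 11.0 | 11% |
| 0.20 | 0.20 | 46% | 8.2 | 18% |
| 0.20 | 0.25 | 53% | 6.8 | 26% |

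With domain 1 removed, the odds ratio is 1.00 in every row. For scale, section 4.4.1 calls 1.6 per SD of a biomarker a moderate effect.

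**4. NICU exposure.** With no carry-over past discharge the built-in odds ratio is 1.00. Suppose instead that a share c of exposed infants still report the drug at month 3 only (m = 0.10, q = 0.20). Their month-3 drug probability becomes m + (1 − m)c. PRD is then 34.5% at c = 10% and 47.0% at c = 50%, against 31.3% in the unexposed. The odds ratios are 1.15 and 1.94. Longer carry-over would raise them.

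**5. Simpler illustrations, also on assumed inputs.** If infants reported on a drug at two interviews have PRD of 100% and all others have p, the risk ratio is 1/p: 3.3 at p = 0.30 and 1.7 at p = 0.60. If two centres share non-drug morbidity of 30% and prescribe at two interviews to 10% and 40% of infants, independently of disease, PRD is 1 − 0.70 × 0.90 = 37% and 1 − 0.70 × 0.60 = 58%.

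**The case against.** The tempting stronger reading is that Aim 3 cannot be answered with the primary outcome at all. The documents do not support it. NICU exposure is charted daily, precedes PRD and never enters it. A drug still in use at discharge need not lead to PRD, because two positive interviews are required. It need not even make the month-3 interview positive: section 2.1 asks about the time since last contact, but section 3.3.1 asks about the previous three months. Three months corrected age is about 53 weeks PMA, so a drug stopped before about 40 weeks could fall outside the second window.

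Aim 3 is also worded as descriptive and does not name PRD, and the study calls itself hypothesis generating. Outcomes without drugs already exist, and the list in 4.3.4 is open. All of this is true and limits the point. It does not remove it. Section 2.1 presents PRD as the composite outcome of morbidity, and the severity score and per-visit indicator repeat its domains. A reader who takes respiratory morbidity in Aim 3 as the protocol defines it therefore meets the overlap each time. An open list permits a drug-free variant but does not commit to one.

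The sizes are weaker evidence than the definitions. The 1/p ratios restate the definition, and they apply an overall incidence that includes drug users to non-users. The 10% versus 40% contrast is assumed, and it supposes that centres drive prescribing after discharge, although section 1 describes infants returning to paediatricians, emergency rooms and pulmonologists.

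The most substantial objection concerns the remedy. Section 2.1 notes that medication may abrogate symptoms. An outcome without medications can therefore class treated, symptom-controlled infants as free of disease. That stands and must be stated with the variant.

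**Conclusion.** The concern holds for post-discharge exposure to the four studied classes. Its association with PRD, the severity score and the per-visit indicator is partly true by definition. That conclusion rests on the protocol's text alone. The size rests on assumptions: an odds ratio of about 4.4 to 17.7 for any versus no post-discharge drug, with independent interviews and no true relation. The 3.3 and 1.7 risk ratios and the 37% versus 58% contrast are likewise illustrations, not protocol figures.

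NICU exposure can be related to PRD, with an allowance for carry-over (about 1.15 to 1.94 in the illustration) and the usual caution about confounding by indication. PRD as the primary outcome and the sample size are not affected. This is a worthwhile, inexpensive clarification.

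**What to change.** In 2.2 and 4.3.4, state that Aim 3 analyses of drug exposure:

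- use a PRD variant without the medication domain, applying the same two-interview rule to hospitalizations, symptoms and home technology, plus qualifying late death;
- report it beside the existing drug-free outcomes, namely respiratory re-hospitalization, and FEF75 in the iPFT subset;
- analyse NICU exposure separately from post-discharge exposure;
- count post-discharge exposure only when it precedes the interval in which the outcome is counted;
- show centre comparisons of PRD with and without the medication domain.

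PRD stays unchanged as the primary outcome.

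**Cost.** Some wording and one derived variable from data already collected. Events become fewer and precision falls: in the illustrations PRD drops from 31% to 18% (m = 0.10, q = 0.20) or from 39% to 26% (m = 0.10, q = 0.25). Infants whose symptoms are controlled by medication may be classed as without disease, so the full-PRD result should stand beside the variant with the overlap noted. The timing rule also limits late exposure: a drug first reported at month 9 leaves only one later interview, too few for the two-interview rule. The variant removes the overlap but not confounding by indication.

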2.3. Study Population

The risk of short and long-term respiratory morbidity in preterm infants is inversely related to gestational age at birth. This is why the PROP investigators will study the most immature infants <29 weeks of gestation in this multi-center protocol. Importantly, infants who die early during their NICU stay will not contribute any data towards the major goal of this project, which is the prediction of post-prematurity respiratory disease up to one year of age. It is readily seen by comparing Tables 2.3.1 and 2.3.2 that one approach might have been to wait until the infants have survived at least 7 days before enrolling them in PROP. This would clearly lessen the loss of study participants due to early mortality from the 1 year cohort of survivors. However, several sites have parallel evaluations of the PROP study participants for their single center protocols that require the collection of biospecimens shortly after birth.

Gestational Age	Percent of total admissions <28 weeks excluding nonviable infants	Mortality to 1 year
23	8%	44%
24	20%	28%
25	22%	15%
26	26%	19%
27	24%	7%

Table 2.3.1 Gestational age distribution of recent admissions at Vanderbilt University, with mortality through the 1st year of life, among infants who survived at least 2 days

Table 2.3.2 Gestational age distribution of recent admissions at Vanderbilt University, with mortality through the 1st year of life, among infants who survived at least 7 days

Gestational Age	Percent of total admissions <28 weeks excluding nonviable infants	Mortality to 1 year
23	5%	17%
24	19%	18%
25	22%	16%
26	28%	13%
27	26%	3%

An alternative approach is to have few restrictions on the probability of the initial survival but to "replace" children who die with new recruits. Therefore, PROP infants who do not survive to 36 weeks PMA will be "replaced" by new participants to achieve the desired target sample size of 750 infants who are likely to survive to one year. The early deaths will be used in the assessment of total mortality as a secondary outcome.

Moreover, early mortality will be strongly correlated with the degree of immaturity (Tables 2.3.1 and 2.3.2). To optimize the numbers of infants who will be available for follow up through the first year of life at each week of gestational age between 23 and 28 weeks, we propose to enroll the PROP study participants in the following 5 strata:

- i. 23 0/7 to 24 6/7 weeks GA
- ii. 25 0/7 to 25 6/7 weeks GA
- iii. 26 0/7 to 26 6/7 weeks GA
- iv. 27 0/7 to 27 6/7 weeks GA
- v. 28 0/7 to 28 6/7 weeks GA

Without this stratification, the final cohort of survivors at 1 year would contain only a small minority of the most immature infants who are born at the margin of viability. One of the greatest benefits of identifying additional biomarkers for respiratory morbidity in the first year of life would be the stratification by risk within gestational age groups with the potential to identify phenotypic subgroups, patient-specific mechanisms and therapeutic targets. It is therefore important to enroll sufficient participants to allow data analysis within gestational age subgroups.

The DCC will monitor the number of infants who survive to 36 weeks PMA in each of the 5 strata. Enrollment into a particular stratum will end as soon as 150 survivors to 36 weeks PMA have been documented.

The most immature infants born at 23 and 24 weeks gestation have been combined into one stratum because the investigators in the 6 clinical sites are concerned that they will not be able to enroll 300 survivors to 36 weeks PMA who are born at these very low gestational ages. However, in the event that enrollment and/or survival at these low gestational ages is higher than anticipated, we will not limit the number of infants in stratum 1 to a total of 150 infants.

2.3.1. Inclusion Criteria

- a. Infants who are less than or equal to 7 days old
- b. Gestational Age (GA) between 23 weeks and 0/7 days and 28 weeks and 6/7 days

2.3.2. Exclusion Criteria

Infants who meet any of the following conditions will be excluded from the PROP cohort:

- a. The infant is not considered to be viable (decision made not to provide lifesaving therapies)
- b. Congenital heart disease (not including PDA and hemodynamically insignificant VSD or ASD)
- c. Structural abnormalities of the upper airway, lungs or chest wall
- d. Other congenital malformations or syndromes that adversely affect life expectancy or cardio-pulmonary development
- e. Family is unlikely to be available for long-term follow-up

We recognize that extremely preterm infants who are born outside of the tertiary care centers and transported into the PROP clinical centers soon after birth have an increased risk of adverse pulmonary outcomes compared with infants who are inborn. However, we intend to study the entire spectrum of respiratory morbidity in the target population and will therefore enroll outborn infants provided the data that are needed for the PROP multi-center core database can be obtained.

3. Study Measurements and Procedures

3.1. Assessments During Hospitalization in the Neonatal Intensive Care Unit

Standardized data collection will include documentation of screening for eligibility and consent as well as pertinent maternal and infant baseline characteristics. Acquired co-morbidities of prematurity will be recorded at a postmenstrual age (PMA) of 40 weeks, or discharge if earlier. Co-morbidity data will include diagnosis and treatment of patent ductus arteriosus (PDA), pulmonary air leak, acquired airway anomalies, culture-proven infections, necrotizing enterocolitis, evidence of brain injury on neuroimaging tests, surgical procedures, and retinopathy of prematurity. In addition, detailed respiratory, growth, nutrition and medication data will be collected daily as described in sections 3.1.1 and 3.1.2. All of these data are routinely recorded in the medical charts of all eligible infants and will be extracted and transmitted to the DCC by the research coordinator

at each clinical site. In addition, a discharge interview will be conducted, where data will be collected with regard to family history of respiratory illness, allergy and atopy, potential environmental exposures and contact information.

3.1.1. Daily Respiratory, Growth, and Nutrition Data

During the infant's hospitalization, clinical data will be collected on a daily basis until 40 weeks PMA, or discharge if earlier that describe use of respiratory supports, duration and amount of exposure to supplemental oxygen and nitric oxide, growth parameters, and feeding status . Respiratory data will be collected on a weekly basis from infants who remain hospitalized beyond 40 weeks PMA.

3.1.2. Daily Medication Data

Data on all commonly used classes of drugs in the neonatal intensive care unit will be collected. For most drugs, the research coordinator will simply record whether or not a particular drug was administered.

However, with additional resources obtained as a supplement from the Eunice Kennedy Shriver National Institute of Child Health and Development (NICHD) under the Best Pharmaceuticals for Children Act, four classes of commonly used respiratory drugs will be studied more extensively with respect to dose and administration, duration of use and adverse effects: diuretics, inhaled bronchodilators, methylxanthines, inhaled and systemic corticosteroids. The PROP investigators will collect detailed data on these specific respiratory medication exposures from birth to one year corrected age in this prospective multi-center cohort of very preterm infants. In the NICU, the daily data collected from the medical record and will include name of medication, route of administration, dose and frequency. This will provide much needed insights into the current use of respiratory drugs in this high-risk population. There are no current evidence-based practice guidelines for most of the respiratory medications that are used in preterm infants. Moreover, the great majority of these respiratory medications are prescribed for this population "off-label". Understanding current drug prescribing practice and its potential variability in this vulnerable population of children will have important implications for the design of future clinical research studies in sick and preterm newborns who are at risk of developing chronic respiratory disease.

3.1.3. **Collection of Biospecimens for a PROP Repository**

The overriding hypothesis for this project is that measurement of selected biomarkers and DNA polymorphisms in this repository of specimens, combined with the robust clinical database, will provide new information related to biological events associated with the pathogenesis and occurrence of post-prematurity respiratory disease (PRD). Although diverse mechanisms contribute to the etiology of chronic lung disease in preterm infants, interactions between developmental and genetic influences are likely to play a role in determining the respiratory outcomes of prematurity.³⁶⁻³⁸ Disruptive genetic variants in pathways mediating structural development, functional development of fluid fluxes, surfactant metabolism, anti-oxidant capacity, or regulation of inflammation and repair, may provide susceptibility to adverse pulmonary outcomes in the face of a developmentally immature lung.

Tracheal aspirate and urine specimens provide a source of potential biomarkers related to pulmonary outcome, and a majority of clinical sites have proposed single-center studies with these samples. Availability of samples from other sites via the repository will allow expanded studies of selected biomarkers of interest. The repositories of tracheal aspirate and urine samples will be available to all PROP investigators for validation of individual site biomarker results in a larger cohort of infants. The repositories will also permit studies of new biomarkers of interest or utilization of new or improved technologies such as proteomics for future biomarker discovery. The repository of DNA from infants and parents will also be available to all investigators for future genotyping studies.

Four centers have proposed projects that involve tracheal aspirate assays or genotyping as part of either their single center or multi-center proposal. Four centers have proposed studies of urinary biomarkers. The rapid changes in sequencing technology will permit acquisition of significantly more sequence data at less cost within the next 3-4 years; the DNA repository is therefore viewed as a resource for PROP investigators to develop additional proposals in later years that utilize the power of this large number of samples and extensive sequencing capacity to address more specific mechanistic/genetic questions. Thus, expected use of the repositories is substantial and the biospecimen along with extensive clinical data provide a novel resource for PROP as well as future investigators. In addition, collection of these three types of biospecimen is relatively straightforward and non-invasive without a major impact on PROP personnel, families, or funding.

All centers will obtain samples of tracheal aspirate, urine and saliva (for DNA extraction) from enrolled infants. In addition, saliva will be obtained from mothers, and fathers when possible, of enrolled infants. Tracheal aspirate and urine samples will be archived in investigator-led laboratories at UCSF and Vanderbilt, respectively. The Center for Human Genetics Research (http://chgr.mc.vanderbilt.edu) at Vanderbilt University will serve as the repository for the DNA specimens. The following samples will be collected from study participants using standardized methods:

- a. Saliva for DNA extraction will be collected preferably during the first week or alternatively later during hospitalization or at the 1-year follow-up visit
- b. Tracheal aspirate samples will be obtained during routine suctioning of intubated patients for clinical purpose
- c. Urine samples will be collected from cotton balls that are placed in the diaper
- d. Tracheal aspirates and urine samples will be collected on the following schedule:
 - o 2 samples at 2-4 days in the first week after enrollment;
 - o 1 sample 7 days later;
 - o 1 sample at 28 days postnatal

